#### **3.1. Randomization**

Group assignment was accomplished with the use of a computer-generated randomization scheme in a 1:1 ratio. Randomization will be stratified for enrolling site and the severity of HF as quantified by the BNP level (below or above 1000 ng/l) or NTpro-BNP level (below or above 4000 ng/l). Patients will be randomized to either the early goal directed group or the control group.

---

**g. Blinding**

Blinding of physicians and patients during hospitalization is not possible/feasible with this specific intervention. However, physicians responsible for the long-term care of patients after the index hospitalization will remain blinded to the group assignment. Also, endpoints will be adjudicated by experts blinded to group assignment.

## h. Study assessments

The following study assessments are planned:

Study assessment schedule	Screening	D1	D2	D3	D4	D5	D6	Discharge	FU	D90	D180	D360
Screening of Patient in Emergency Department	S/I											
Check Inclusion/ Exclusion Criteria	S/I											
Inclusion: Patient signed the Informed Consent	S/I											
Inclusion: Randomize Patient in Secu Trial	S/I											
No inclusion: Enter Patient in " Screening Enrolment Log"	S/I											
HF assessment	S/I											
Measure vital signs 0h/ 30min/ 1h/2h/3h/4h/6h	S/I											
Give oral Capsule of Nitroglycerine (1)		I										
Apply the nitro patches according to the blood pressure		I										
Increasing nitro patches according to BP, stick for 24hrs (2)			I									
Reduction of nitro patches according to BP (2)			I	I	I	I						
Give one oral Hydralazine Tbl à 25mg every 6hours		I										
Collect Urine and Blood Samples		S/I	S/I	S/I			S/I					
Dyspnea Assessment		S/I	S/I				S/I	S/I				
Edema measurement		S/I					S/I					
Hand out the QOL and KCCQ Questionnaire				S/I						S/I	S/I	S/I
Collected the QOL and KCCQ Questionnaire					S/I					S/I	S/I	S/I
Actively search for AE's/ SAE's			S/I	S/I			S/I			S/I	S/I	S/I
Ask about Patient's Health status										S/I	S/I	S/I
Ask for medication										S/I	S/I	S/I
Ask about Dyspnea										S/I	S/I	S/I
Rehospitalization (3)										S/I	S/I	S/I

S= Standard group/ I= Interventions group

(1) every 10min x 3times

(2) target systolic BP  $\leq$ 110mmHg

(3) SAE, yes/no?

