### Important Treatment Rules

- ACE-inhibitor can be administered once or twice per day. ARB should be administered only once a day.
- If Patient is already on ACE-inhibitor or ARB continue dosage unchanged during day 1 and perform up-titration following day 2 till 7 schedule.
- If the patient is already treated with another ACE-inhibitor / ARB than listed in the schedule, previously prescribed ACE-inhibitor / ARB should be continued unchanged during day 1. A daily up-titration of approximate 50% (25% to 75% depending on blood pressure response) starting from day 2 is recommended. The maximal dosage should be achieved at day 5 to 7 of treatment if well tolerated.
- If creatinine levels rise more than 50% from baseline continue ACE-inhibitor / ARB in unchanged dosage to creatinine levels begin to decline. Then continue up-titration according to the treatment schedule.
- If creatinine levels rise more than 100% from baseline reduce ACE-inhibitor / ARB treatment by 50% and continue therapy with unchanged dosage until creatinine levels decline more than 30%.
- Treatment with any diuretics or aldosterone-antagonists at any time is at discretion of treating physician and not determined by the study protocol.

**Figure 5a:** Treatment algorithm for the early goal-directed therapy group (continuation).

On day 3 a further up-titration of the ACE-inhibitor / ARB depends on systolic blood pressure according to Figure 5a will be performed. In patients on LCZ696, the dose of LCZ696 remains unchanged. The dosage of transdermal nitrates will be gradually decreased from day 3 till hospital discharge (Figure 5a). Also, intermittent dosing (12 hours nitrates, 12 hours nitrate-free period) will be used from day 3 on. Typically, we would use in half the dose applied at day 2 and apply the patches from 8:00 h am till 8:00 h pm.

On day 4 till day 7 a further up-titration of the ACE-inhibitor / ARB dependent on systolic blood pressure according to Figure 5a will be performed. In patients on LCZ696 the dose of LCZ696 will be up-titrated by again 25% if not already on target dose (200 mg twice daily).

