Transthoracic echocardiography (TTE) for the detailed assessment of systolic, diastolic, and valvular function will be performed as clinically indicated in the majority of patients. Response to therapy will be documented by daily clinical patient assessment using a predefined questionnaire as well as a visual analogue scale to record subjective course of dyspnea. Periodical measurements of electrolytes (sodium, potassium) and creatinine at study inclusion, every 24 to 72 hours during the first week and at discharge will be accomplished.

In the further course of treatment (usually one or two days before discharge), a beta-blocker will be added to this therapy at very low dose. Augmentation of the beta-blocker dosage will only be performed after discharge during the outpatient phase. Spironolactone (an aldosteron-receptor-antagonist) may be added in patients who remain in NYHA classes III and IV and in patients with low potassium concentration at presentation, as long as they have a serum creatinine below 150 µmol/l.

Despite early blood pressure intervention in the study group, special attention will be given to the final drug-treatment in both study groups. As ACE-inhibitors / ARB and beta-blockers provide the best documented survival benefit in patients with HF (3,7), initiation of a beta-blocker before hospital discharge will be strongly endorsed, and treatment of an equal percentage of patients in both arms with these two agents remains crucial.

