## 11. Evaluation of safety parameters

### ff. Adverse events

Specific adverse events (AE) will be documented and investigated only during the course of

	Intervention arm (N=)	Standard of care arm (N=)
--	--------------------------	------------------------------

---

the index hospitalization (see “11.1.1.Brief summary of adverse events”). Additionally, during the first 180 days, all serious adverse events (SAEs) as defined by current Good Clinical Practice standards will be collected, fully investigated and documented in source documents and case report forms (CRF). Study duration encompasses the time from when the participant signs the informed consent until the last protocol-specific procedure has been completed (last FU at 360 days).

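### No adverse event search is scheduled at discharge, on D4–D5 or after D6, so headache, dizziness and falls in hospital may be under-recorded to a degree that depends on length of stay

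*Combined protocol and SAP*

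**What the plan says.** The schedule in SAP section 3.5 (headed h. Study assessments) marks the row "Actively search for AE's/ SAE's" for both arms at D2, D3, D6, D90, D180 and D360. D1, D4, D5 and Discharge are empty. The dyspnea row of the same grid does carry a Discharge mark.

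SAP section 11.1 (ff. Adverse events) limits the listed events to the index hospitalization: "Specific adverse events (AE) will be documented and investigated only during the course of" that stay. Serious events have a longer window: "during the first 180 days, all serious adverse events (SAEs) as defined by current Good Clinical Practice standards will be collected".

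Protocol section 5 continues the intervention-arm titration past the D3 search: "On day 4 till day 7 a further up-titration of the ACE-inhibitor / ARB". For drugs outside the schedule it adds: "The maximal dosage should be achieved at day 5 to 7 of treatment if well tolerated".

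For both groups the protocol also plans other contacts. It states "Response to therapy will be documented by daily clinical patient assessment using a predefined questionnaire", together with a dyspnea scale. It plans electrolytes and "creatinine at study inclusion, every 24 to 72 hours during the first week and at discharge will be accomplished". Hemodynamic monitoring continues every 6 to 8 hours for the rest of the stay. SAP section 11.3.1 lets the dyspnea assessment fall on day six or at discharge, whichever is earlier. No such rule is given for adverse events.

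**The concern.** Safety is part of the stated hypothesis, and SAP section 11.1.3 compares the arms on events per patient. Some listed events leave no laboratory or monitoring trace and come to light mainly when someone asks. For these, a day in hospital followed by a scheduled search before discharge is better covered than a day with none.

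Under the grid, a patient who leaves on D4 or D5 is last asked on D3, and a patient who stays beyond D6 is last asked on D6. After discharge the non-serious events are out of window. The trial is open label in hospital (SAP section 3.4), so whatever is recorded outside a scheduled search is recorded by staff who know the arm. The completeness of the symptom data then varies with length of stay, which is itself an outcome: the protocol introduction expects the intervention to shorten it.

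**Working it through.** The plan states no figure on this point, so there is none to reproduce. The check has three steps.

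**1. Days after the last in-hospital search.** Inputs: search days 2, 3 and 6 (SAP section 3.5). Let L be the day of discharge, counted as a stay of L days, and s(L) the latest search day not after L. A search due on the day of discharge is assumed to be done before the patient leaves. Uncovered days = L − s(L). Share = (L − s(L))/L.

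| Discharge day L | Last search s(L) | Days after it | Share of stay |
|---|---|---|---|
| 2 | 2 | 0 | 0% |
| 3 | 3 | 0 | 0% |
| 4 | 3 | 1 | 1/4 = 25% |
| 5 | 3 | 2 | 2/5 = 40% |
| 6 | 6 | 0 | 0% |
| 7 | 6 | 1 | 1/7 = 14% |
| 8 | 6 | 2 | 2/8 = 25% |
| 10 | 6 | 4 | 4/10 = 40% |
| 14 | 6 | 8 | 8/14 = 57% |

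The gap is not monotone in length of stay: it is zero at 2, 3 and 6 days and positive on either side of 6. These shares need no assumption about detection rates.

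**2. Search days against titration.** Ramipril in protocol Figure 5a, lowest to highest over the blood pressure bands, as a percentage of the table's 10 mg ceiling:

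- D2: 1.25–2.5 mg, 12.5–25% (search)
- D3: 2.5–5 mg, 25–50% (search)
- D4: 3.75–7.5 mg, 37.5–75% (none)
- D5: 5–10 mg, 50–100% (none)
- D6: 7.5–10 mg, 75–100% (search)
- D7: 10 mg, 100% (none)

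So D6 is a searched high-dose day. The high-dose days without a later in-hospital search are D7 onward, and D5 for patients discharged that day. For patients still in hospital on D6, that search can look back over D4 and D5.

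**3. Which listed events are exposed to the gap.** SAP section 11.1.1 lists eleven:

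- Creatinine rise, hypokalemia and hyperkalemia (3): scheduled laboratory tests, including one at discharge.
- Hypotension (1): monitoring every 6 to 8 hours throughout the stay.
- Arrhythmia requiring therapy, acute coronary syndrome, ICU transfer and resuscitation (4): each leads to clinical action and would not normally depend on questioning.
- Headache, dizziness and fall (3): found largely by asking.

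The count is 3 + 1 + 4 + 3 = 11, so the gap bears mainly on 3 of 11 items.

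**The case against.** **The grid is a summary and is visibly incomplete.** Blood samples and edema have no Discharge mark although the protocol text requires both at discharge, and hydralazine is marked on D1 only although it runs for 48 hours. A blank cell therefore does not prove that nothing is done. This stands, and it weakens the contrast with the dyspnea row. But for those rows other text supplies the missing time point. For the adverse event search no text does.

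**Recording is a standing duty and staff see patients daily.** Protocol section 10.6.2 obliges investigators to record adverse events, and there is a "daily clinical patient assessment using a predefined questionnaire". Both stand. However, that questionnaire is described as documenting response to therapy, and nothing says that it asks about adverse events.

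**The search days follow the exposure period.** SAP section 8.2.2 puts exposure at six days or until discharge. Hydralazine ends at 48 hours, Figure 5a lists no nitrate on days 6 and 7, and safety-population events are reported only to the last hydralazine or nitrate intake. So days after D6 matter little for that analysis, and nitrate headache belongs mostly to the early, searched days. The argument does not cover discharges on D4 or D5. Nor does it cover the intention-to-treat comparison, since the listed events are collected over the whole index stay and the ACE-inhibitor/ARB titration goes on to day 7.

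**A stronger reading: the arm comparison is biased.** A reader might infer this from the expected shorter stay in the intervention arm. The documents do not support it. The schedule is identical in both arms, and neither length-of-stay data nor detection rates are given. Suppose that active search finds 95% of events and other recording 50% (assumptions). If every patient stays exactly 5 days in one arm and 6 in the other, capture is (3 × 0.95 + 2 × 0.50)/5 = 0.770 against 0.950, a ratio of 0.81. If stays are spread around the same means (assumed gamma, coefficient of variation 0.4 to 0.8), the ratio is about 1.02 to 1.03. The sign changes with an assumption that the documents cannot settle, so no ratio should be quoted.

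**Conclusion.** The point holds as a gap in the schedule. Following the plan as written, discharges on D4 or D5 have no scheduled adverse event search after D3, and longer stays have none after D6. The uncovered share is 25% to 40% of the stay for D4–D5 discharges, and it rises from 14% at 7 days to 57% at 14 days. It is zero for discharge on D2, D3 or D6. The consequence is possible under-recording of symptomatic events, mainly headache, dizziness and falls.

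Two further readings go too far. The highest-dose days are not all unsearched, because D6 is both a search day and a high-dose day. And the listed events as a group do not depend on spontaneous reports, because most have laboratory, monitoring or clinical routes. Serious events can also still be picked up at D90 and D180.

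The number of events missed and the size and direction of any difference between arms are unknown. The conclusion rests on reading the grid and text as complete for this one item. If a discharge check is in fact made, the remaining problem is only that the SAP does not say so. Severity: minor.

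**What to change.** Mark the adverse event search in the Discharge column of the SAP 3.5 grid for both arms. Let it cover the time since the last search, and record the day of onset of each event. It can be done at the discharge assessment that already takes place. State the same rule in SAP section 11.1. The daily assessment in the protocol could carry the same items, but that is optional.

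For patients already treated, tabulate the listed events by onset day, where it was recorded, and by whether a scheduled search followed before discharge. State the limitation beside the symptom rows of the adverse event table.

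Cost: a small CRF change and a few minutes per patient. It needs no new visit or procedure and does not change treatment.

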## **4. Data management**

### **i. Data export**

Initially, data from Basel site were captured into an Access (Microsoft, USA) and data from external centers into SINATRAS EDC software (developed by SAKK). As from April 2016, new data for all the centers participating in this trial were captured inside the secuTrial EDC system and former data imported to the same EDC at the Clinical Trial Unit of the University Hospital Basel reassuring that the outcome measures remain independent from the investigators.

SecuTrial EDC system:

<https://secutrial.insel.ch/apps/WebObjects/ST21-productive-DataCapture.woa/wa/>

Data will be exported using the secuTrial data export tool:

<https://secutrial.insel.ch/apps/WebObjects/ST21-productive-ExportSearchTool.woa/wa/>

Data are exported as comma delimited files, and are labelled using the codebook provided by secuTrial in the same export.

### **j. Data validation**

The following data validation checks will be performed:

1. For critical items, univariate, multivariate and cross-module checks will be performed. This will include valid-value (e.g. selections of only “yes” or only “no”), valid-range (e.g. range of vital signs), and missing-value (e.g. age).
2. Occurrence of events or items containing dates, will be checked whether they occurred on/after the date of randomization with the only exception being items from the medical history (e.g. date of previous stroke, previous echocardiogram) which could have occurred before the randomization.

## 5. Study populations

### k. Patient flow

The number of patients randomized will be taken from the randomization eCRF and the following flow chart will be produced:

[figure not shown]

Figure 1 Study Flowchart

## **I. Definition of populations for analysis**

All patients attending to the ED with acute decompensated heart failure will be pre-screened by the local Investigators. Each potential candidate will be individually assessed for inclusion and exclusion criteria. If the candidate qualifies, he or she will be invited to participate in the GALACTIC Trial.

### **m. Intention- To -Treat (ITT)**

The intention to treat population consists of all patients randomized. The primary and secondary endpoints of patients randomized to early goal-directed decrement of preload and afterload (intervention group) will be compared to the patients randomized to standard of care by the intention-to-treat principle.

Patients without a follow-up assessment at 6 months for the primary endpoint will be censored at the time of the last follow-up information available.

### **n. Per-protocol (PP)**

The per-protocol population PP consists of all patients randomized, who received at least one dose of the study drug (Hydralazine and/or nitrates in the form of capsules, spray and/or transdermal application) and had a baseline plus follow-up assessment (180 days) of the primary endpoint completing the study without major protocol deviations. PP analyses are planned as part of sensitivity analyses.

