## Study Therapy Early Goal-Directed Group

Early goal-directed preload and afterload decrement with a target systolic blood pressure of 90 mm Hg to 110 mm Hg for the entire hospitalization. This blood pressure target is considered to represent the maximal feasible afterload decrement without impairment of critical organ perfusion (40). This pathophysiologic goal is pursued by predominately applying nitrates, ACE-inhibitors and ARBs at maximal tolerable (avoiding arterial hypovolemia and inadequate arterial perfusion pressure) doses.

The treatment schedule is displayed in Figure 5a. Accordingly, on day 1 (0 h till 24 h) treatment will be started with one capsule of sublingual nitrates (containing usually 0.8 mg glyceryl trinitrate) or two applications of nitrospray (containing usually 0.4 mg

glyceryl trinitrate per application) in combination with transdermal nitrates (for example Nitroderm TTS® 10 mg / 24h) in a dosage between 40 to 80 mg / 24 h depending on admission systolic blood pressure. 10 and 20 minutes after the initial sublingual nitrates capsule or nitrospray application, one additional capsule of sublingual nitrates (containing usually 0.8 mg glyceryl trinitrate) or two applications of nitrospray (containing usually 0.4 mg glyceryl trinitrate per application) will be administered (in total three capsules sublingual nitrates or six applications of nitrospray). After 6 hours a dose adjustment of the transdermal nitrates dependent on systolic blood pressure will be performed (Figure 5a). On day 1 and 2, transdermal nitrates will be applied as continuous therapy for 24 hours each patch. In patients without severe renal dysfunction (defined as calculated glomerular filtration rate below 30 ml/min) and without evidence of an acute coronary syndrome (accompanying chest pain, new ECG changes, elevated cardiac Troponin T), hydralazine will be added orally to achieve an early maximal vasodilative effect and to avoid tolerance to nitrates. Hydralazine will be administered in a fix dosage of 25 mg every 6 hours (1 - 1 - 1 - 1) for the first 48 hours after study inclusion. Patients with evidence for an acute coronary syndrome (Cave: “coronary steal”) or with severe renal dysfunction (Cave: accumulation) will not receive hydralazine, but nitrates only.

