### **Study Therapy Control Group**

The current guidelines of the European Society of Cardiology do not recommend the use of ACE-inhibitors or ARB in the early stabilization of patients with acute HF (41). (37). The administration of previously prescribed ACE-inhibitors or ARB should be continued on admission with AHF, except in the presence of hemodynamic instability, hyperkalemia or severely impaired renal function. In these cases, the daily dosage of oral therapy may be reduced or stopped temporarily until the patient is stabilized. In the absence of a prescription, an initiation of the medication before discharge from hospital and up-titration every two to four weeks is recommended (37). Accordingly, patients in the control group will receive (1,2) oxygen application, treatment with diuretics based on extent of fluid overload and recent weight gain. The dosage thereby will be adjusted to renal function. Further on, after 24 to 48 hours, treatment with an ACE-inhibitor (or ARB) will be started in low dosages displayed in Figure 5b. After six to eight days of treatment, dosage of the ACE-inhibitor / ARB will be up-

titrated following the schedule displayed in Figure 5b dependent on hemodynamic and renal tolerance. As in the Intervention group, in patients with chronic HF and a LVEF below 35%, the treating physician may at any time (both in-hospital and after hospitalization) consider to replace a preexisting therapy with an ACE-inhibitor or ARB with LCZ696 as recommended in the 2016 ESC guidelines (36). Should the patient already be on LCZ696 (“Entresto”), the dosage will remain unchanged for the first 4 to 5 days with the option of increasing the dose by 25% at the end of hospitalization (if not already at 200 mg b.i.d).

Transdermal nitrates can be used, but only in the doses currently approved in Switzerland (e. g. Nitroderm TTS 5 mg / 12 h or 10 mg / 12h). The use of nitrates or hydralazine in higher doses is strongly discouraged. The use of a specific blood pressure target is up to the discretion of the treating physician.

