Should the patient be already treated with another ACE-inhibitor / ARB not listed in the therapy schedule (Figure 5b), again the previously prescribed ACE-inhibitor / ARB will be continued in an unchanged dosage if tolerated for the first two to three days after which up-titration will then be performed in a comparable way like demonstrate for the ACE-inhibitors / ARBs listed in Figure 5b. Accordingly up-titration of 50% will be performed every seven to 21 days to the maximum tolerated dose in order to achieve adequate inhibition of the renin–angiotensin–aldosterone system (37).

Control group	Starting dose (mg)	Target dose (mg) * if patient is still hospitalised
transdermal Glyceryl trinitrate (i.e. Nitroderm® TTS) [mg / 12 h]	0 - 10	0 - 10
Ramipril (i. e. Triatec®) [mg/d] 	2.5 o.d.	10 o.d.
Lisinopril (i. e. Zestril®) [mg/d] 	2.5–5.0 o.d	20–35 o.d.
Enalapril (i. e. Reniten®) [mg/d] 	2.5 b.i.d.	20 b.i.d.
Captopril (i. e. Capoten®) [mg/d] 	6.25 t.i.d.	50 t.i.d.
Candesartan (i. e. Atacand®) [mg/d] 	4–8 o.d	32 o.d
Losartan (i. e. Cozaar®) [mg/d] 	50 o.d.	150 o.d.

 Only one ACE-inhibitor should be started.  
 ARB will only be initiated if ACE-inhibitor intolerance is known.

**Figure 5b:** Treatment algorithm for the control group as recommended by the current ESC guidelines.

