### **o. As Treated (AT)**

The as treated population AT consist of all the patients randomized analyzed not to the allocation group but according to the treatment they actually received. No AT analyses are currently planned.

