### **q. Definition of sub-group populations in different analyses**

Predefined subgroups are as follows: patients younger versus older than 75 years of age, men versus women, HF with reduced LVEF (LVEF< 40%) versus HF with mid-range LVEF (LVEF 40-49%) versus HF with preserved LVEF (LVEF≥50%), systolic blood pressure at randomization lower versus ≥120 mmHg, coronary artery disease present or not, BNP

---

 Major protocol deviations defined as the disclosure of exclusion criteria after enrollment.

concentration at randomization lower or  $\geq 1000$  pg/ml, patients with versus without known chronic heart failure, and estimated glomerular filtration rate  $< 60$  ml/min versus  $\geq 60$  ml/min.

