### **v. Methods for handling missing data and sensitivity analyses**

Sensitivity analyses will be conducted in: patients without evidence of systemic, infection/inflammation at presentation (defined as CRP  $< 20$  mg/L), in patients without major protocol deviation and in patients enrolled in outside Europe and Central Europe.

To deal with data with  $> 10\%$  missing values, sensitivity analyses will be conducted using multiple imputations by chained equations methods and 20 data-sets will be created.

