**ii. Adjustments for covariates**

The primary analysis will be adjusted for four strong predictors of the composite primary endpoint (death or HF-rehospitalisation within 6 months): age, HF hospitalization in the year before inclusion, systolic blood pressure, and serum creatinine.

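### The per-protocol set requires a dose of hydralazine or nitrate without limiting this to the intervention arm, so as written it selects controls by a treatment chosen after randomisation

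*Combined protocol and SAP*

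**What the plan says.** **Per-protocol rule (SAP 5.4).** The set is restricted to randomised patients who "received at least one dose of the study drug (Hydralazine and/or nitrates in the form of capsules, spray and/or transdermal application"), with a baseline and a 180-day assessment of the primary endpoint and no major deviation. No arm is named. Its footnote 2 reads "Major protocol deviations defined as the disclosure of exclusion criteria after enrollment". Receiving, or not receiving, a drug is therefore never a major deviation. The analysis is a sensitivity analysis.

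**Intervention arm (protocol section 5, Early Goal-Directed Group).** On day 1 "treatment will be started with one capsule of sublingual nitrates" (or spray), together with patches at 40 to 80 mg per 24 h.

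**Control arm (protocol section 5, Control Group).** "Transdermal nitrates can be used, but only in the doses currently approved in Switzerland". Higher doses of nitrate or hydralazine are discouraged. Figure 5b, captioned "Treatment algorithm for the control group as recommended by the current ESC guidelines", gives the patch dose as 0 to 10 mg per 12 h for both starting and target dose, and has no hydralazine row. A control with no nitrate is fully within protocol, and so is one on a 5 or 10 mg patch.

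**Related text.** SAP 6.5 lists a sensitivity analysis "in patients without major protocol deviation", with no dose condition, and does not say whether this is the per-protocol analysis. SAP 5.6 requires at least one dose of the randomised study drug for the safety population, and SAP 11.1.3 spells this out as hydralazine and/or nitrates, again without naming an arm.

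**The concern.** A per-protocol analysis is meant to compare patients who were treated as their arm specified. Here the dose condition is met almost automatically in one arm and only at the physician's discretion in the other. The intervention group stays nearly whole, while the control group is cut down to those given a vasodilator.

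That choice is made after randomisation and for clinical reasons. Blood pressure is an obvious one, and SAP 6.6.2 lists it among the strong predictors of the primary endpoint ("age, HF hospitalization in the year before inclusion, systolic blood pressure, and serum creatinine"). The retained controls may therefore differ in prognosis from controls as a whole, in a direction that cannot be known in advance. The sensitivity analysis could then appear to support or contradict the main result through selection alone, and with fewer controls than it needs.

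**Working it through.** **Step 1. What each reading of the rule keeps**

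| Reading of SAP 5.4 | Intervention arm | Control arm |
|---|---|---|
| Literal: any hydralazine or nitrate, either arm | nearly all | only controls given some |
| Study drug means the intervention regimen only | nearly all | none |
| Dose required in the intervention arm only (not written) | nearly all | all, before other exclusions |

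Only the third row gives a usable comparison, and the SAP does not state it.

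**Step 2. Inputs for an illustration**

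- From the documents: 385 per arm, 80% power, 5% level, 20% decrease, log-rank test (protocol 8.3 and SAP section 3, Sample size), two-sided (protocol 8.2).
- Not in the documents: the control event rate p, the share q of controls given any nitrate or hydralazine, and r, their risk relative to all controls.
- Simplifications: constant hazards, 385 in the intervention arm, other per-protocol exclusions ignored.

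**Step 3. Reproduce the plan's figure to obtain a working p**

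Take the 20% as a relative reduction in risk. With p = 0.4927 the intervention rate is 0.8 × 0.4927 = 0.3942.

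- HR = ln(1 − 0.3942) / ln(1 − 0.4927) = 0.738.
- Schoenfeld events needed = 4 × (1.960 + 0.842)² / (ln 0.738)² ≈ 341.
- Events expected = 385 × (0.4927 + 0.3942) ≈ 341.

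So 385 per arm is reproduced at a control rate of about 49%. This p is back-solved and remains an assumption.

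**Step 4. Controls kept under the literal rule: 385 × q**

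- q = 10%: 38.5, about 39.
- q = 30%: 115.5, about 116.
- q = 50%: 192.5, about 193.

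**Step 5. Distortion when there is no true effect**

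The intervention arm then has the risk p of all controls, while the retained controls have risk r × p. The per-protocol HR is ln(1 − p) / ln(1 − rp).

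| p | r = 0.9 | r = 1.1 |
|---|---|---|
| 0.4927 | 1.158 | 0.869 |
| 0.40 | 1.145 | 0.881 |
| 0.30 | 1.133 | 0.891 |

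At p = 0.4927, r = 0.8 gives 1.354 and r = 1.2 gives 0.759. Simulated Cox fits at q = 30% gave 1.38 and 0.76. If the planned effect (HR 0.738) were true, r = 0.9 and 1.1 would give 0.738 × 1.158 = 0.855 and 0.738 × 0.869 = 0.642.

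**Step 6. Precision with no selection (r = 1) and no effect**

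SE of ln HR = √[1/(385p) + 1/(385qp)], p = 0.4927; the 95% interval around HR = 1 is exp(±1.96 × SE).

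| q | SE | 95% interval |
|---|---|---|
| 100% (no controls dropped) | 0.103 | 0.82 to 1.22 |
| 50% | 0.126 | 0.78 to 1.28 |
| 30% | 0.151 | 0.74 to 1.34 |
| 10% | 0.241 | 0.62 to 1.60 |

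**The case against.** **The rule may be intended for the intervention arm only.** SAP 8.2 lists sublingual nitrates, hydralazine and 40 to 80 mg patches under the intervention arm and gives controls guideline care; SAP 5.6 speaks of the randomised study drug. A control's low-dose patch would then be background care. This is a fair account of the probable intention, but the written condition applies to every randomised patient, so on that reading no control qualifies. It supports a correction and does not rescue the text.

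**SAP 6.5 has no dose rule.** If that analysis is the one run, no compliant control is lost for want of a dose. This is real mitigation. But SAP 5.4 still stands beside it, and two analysts could produce two different sets.

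**The magnitude is assumed.** This stands. The share dosed, their relative risk and the event rate are not in the documents, and the hazard ratios follow directly from the assumed risk difference. Adjustment for the four covariates in SAP 6.6.2 would remove part of any bias, to the extent that those covariates explain who was given nitrate.

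**Two stronger readings that a reader might infer.** One is that the rule retains crossovers and discards adherent controls. The documents do not support this: a control on a 5 or 10 mg patch is as compliant as one on none, so the retained group is not necessarily one of deviators. The other is that the lack of a planned table of in-hospital nitrate and hydralazine use by arm is part of the same error. SAP Table 2 does cover only baseline, 180 and 360 days, and "No AT analyses are currently planned". But an exposure table is a reporting choice: blood pressure over the first 6 days is planned by arm, and the SAP flow chart, which may show treatment received, is not reproduced in the available text.

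**Conclusion.** The per-protocol definition is wrong as written. It either selects controls by physician-chosen, post-randomisation nitrate or hydralazine use, or excludes all of them. That conclusion rests on the text alone.

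The size is not determined by the documents. Under the stated assumptions, a 10% difference in risk between retained and all controls moves a null per-protocol hazard ratio to 1.16 or 0.87 at a 49.3% event rate, and to 1.13 or 0.89 at 30%. If 30% of controls were dosed, the 95% interval would widen from 0.82–1.22 to 0.74–1.34. The direction of any bias is unknown.

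The consequence is confined to secondary uses. The primary analysis is by intention to treat on all randomised patients and is not affected. The same dose condition sits in the safety population, although SAP 11.1.3 also compares adverse events by intention to treat.

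**What to change.** 1. **SAP 5.4.** Replace the definition with: *The per-protocol set consists of all randomised patients who had a baseline and a 180-day assessment of the primary endpoint and completed the study without major protocol deviations. Patients randomised to the intervention arm must also have received at least one dose of hydralazine and/or nitrates. No dose is required in the standard of care arm.*
2. **SAP 6.5.** State that the analysis in patients without a major deviation uses this set.
3. **SAP 5.6 and 11.1.3.** Apply the dose condition to the intervention arm only. Because SAP 11.1.3 counts events up to the last confirmed intake of study drug, also state the counting window for controls, who may have no intake.

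These are wording changes. They need no new data and leave control care and the primary analysis as they are. They do not remove crossover: a control given hydralazine or high-dose nitrate stays in the set, because the definition of a major deviation is unchanged.

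Optional, as a reporting addition: a descriptive table by arm of in-hospital nitrate and hydralazine use and dose, with the number of patients with data. The CRF summary in protocol 8.1 does not mention in-hospital drug doses, so control doses may need chart abstraction.
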